1.1. Synopsis

Protocol Title: A Phase 2, Parallel, Comparator-Controlled Trial to Evaluate the Safety and Efficacy of LY3209590 in Insulin-Naïve Patients with Type 2 Diabetes Mellitus

Short Title: A Study of LY3209590 in Participants with Type 2 Diabetes Mellitus

Rationale:

This study will evaluate LY3209590 in insulin-naïve patients with type 2 diabetes mellitus (T2DM), compared with insulin degludec.

The study will last 26 weeks to have an adequate duration of exposure necessary to positively exclude any increase in ALT, as has been observed with a previous daily pegylated basal insulin lispro with a predominantly hepatic pharmacodynamic (PD) profile.

Insulin degludec is an unblinded active comparator in this study and will be used to compare the effects of LY3209590 on glycemic control, hypoglycemia, and weight gain with a daily basal insulin.

Objectives and Endpoints

Objectives	Endpoints
Primary	

 To investigate the efficacy of LY3209590 compared with insulin degludec in study participants with T2DM 	
 HbA1c change from baseline to Week 26
Secondary	
Efficacy 
 To investigate the efficacy of LY3209590 compared with insulin degludec in study participants with T2DM 	
 HbA1c change from baseline to Week 12 Fasting glucose change from baseline to Weeks 12 and 26
Safety 
 To investigate the safety of LY3209590 compared with insulin degludec in study participants with T2DM 	
 Incidence and rate of hypoglycemia events during the treatment period Incidence of treatment-emergent serious adverse events
Pharmacokinetics 
 To characterize the PK of LY3209590 and potential intrinsic and extrinsic factors in study participants with T2DM 	
 Steady state AUC at Week 26

Abbreviations: AUC = area under the curve; HbA1c = hemoglobin A1c; PK = pharmacokinetics; T2DM = type 2 diabetes mellitus.

Overall Design:

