Study I8H-MC-BDCL is a multicenter, randomized, open-label, parallel, comparator-controlled Phase 2 study with 3 study periods. The study is designed to evaluate the efficacy and safety of LY3209590 compared with insulin degludec in patients with T2DM treated with a stable dose of metformin (alone or in combination with a stable dose of a DPPIV inhibitor and/or a SGLT2 inhibitor) for at least 3 months prior to screening.

Disclosure Statement: This is a parallel, open-label, treatment study with 2 groups.

Number of Participants:

Approximately 250 participants will be randomly assigned to study interventions such that approximately 200 evaluable participants complete the study.

Intervention Groups and Duration:

Participants will be randomized in a 1:1 ratio to receive the interventions listed below:

[figure not shown]
- LY3209590 subcutaneously weekly, dosed per Algorithm 1(Paper)
- Insulin degludec subcutaneously daily, dosed per a modified Riddle algorithm

The maximum total duration of study participation for each participant is up to 33 weeks, across the following study periods:

- Study Period 1: screening and lead-in period, approximately 2 weeks
- Study Period 2: treatment period, 26 weeks
- Study Period 3: safety follow-up period, 5 weeks

Data Monitoring Committee: No

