Participants who continue to be eligible for the study will be randomized to 1 of the 2 treatment groups. All measures, including a urine pregnancy test, to be performed at Visit 3 (see Schedule of Activities, Section 1.3) should be done prior to injection of the participant's assigned investigational product (IP) to ensure that appropriate baseline measurements are obtained. The FGM sensor should also be removed prior to study treatment and data from the sensor uploaded by the site. The participant will begin IP if the urine pregnancy test is negative. If the result of the serum pregnancy test is positive, the participant will be discontinued from the study (see Section 7.2).

Study personnel will inject the first dose of IP at the study site. The PK sample and electrocardiograms (ECGs) at randomization must be collected as described in the Schedule of Activities (Section 1.3).

Treatment

Following randomization, participants will participate in a 26-week treatment period.

For patients randomized to the LY3209590 group the following guidance for IP administration is applicable:

- During Weeks 0 to 8, site personnel will administer IP at the site. Participants will receive education and training on how to self-administer IP (for details, see the Schedule of Activities). The training should include information on reconstitution of IP, appropriate injection site locations, injection technique, and the signs and symptoms of local adverse reactions, should those occur.
- During Weeks 9 to 12, IP will be reconstituted and administered at the site by the participant, under supervision of trained site personnel to assure that the participant is capable of self-administration.
- During Weeks 13 to 25, outside of titration visits IP can be self-administered by the participant at home unless local regulations require administration at the site, or optionally can be administered once weekly by site personnel.
- Information on self-injection can be reviewed as necessary throughout the study. Additional visits to ensure correct dosing, titration, and study drug administration can occur anytime during the study if deemed necessary by the investigator.

LY3209590 will be administered as follows:

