6.7.1. Treatment after Study Completion

The last study treatment administration for patients treated with LY3209590 will be at Week 25 and for patients treated with insulin degludec the evening before the last study visit at Week 26. The washout of LY3209590 may take up to 10 weeks to complete. Any appropriate antihyperglycemic treatment must therefore be instituted slowly and under regular supervision of blood glucose profiles after discontinuation of LY3209590. If another basal insulin is used as a replacement for LY3209590 or insulin degludec, insulin therapy will be instituted using the Riddle algorithm as needed based on FG (Section 10.8). Since CCI

Therefore, a slow up-titration of another basal insulin is necessary to prevent hypoglycemia due to overlapping insulin action. For example, no insulin would be required until the study participant's blood glucose increases to >100 mg/dL, and then daily basal insulin would be initiated and adjusted based on FG.

Study participants assigned to the insulin degludec treatment group will switch to another glucose lowering regimen per investigator guidance after the last study treatment administration. If they switch to an insulin treatment and insulin degludec is chosen, they can continue with the same dose used until Visit 20 of the study. If they switch to another basal insulin (e.g., insulin glargine), study participants should inject a daily dose, which is 20% lower than the last dose of insulin degludec used before Visit 20 and titrate under supervision of the investigator using the country-specific label for their pre-study basal insulin.

7. Discontinuation of Study Intervention and Participant Discontinuation/Withdrawal

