5.10.1. Study Drug Exposure

Exposure in days in the study will be calculated for each patient and summarized by treatment group. Exposure during the treatment period will be calculated from date of first study basal insulin dose collected in the electronic case report form (eCRF) to date of discontinuation from study treatment (i.e., the last dose date for insulin degludec, and the last dose date + 7 days for LY3209590). The sum of exposure in total patient years will also be provided.

Frequency of subjects falling into the following different exposure ranges will also be summarized: >0 days, ≥ 7 days, ≥ 14 days, ≥ 30 days (1 month), ≥ 60 days (2 months), ≥ 90 days (3 months), ≥ 120 days (4 months), ≥ 183 days (6 months) days.

In addition, the duration of follow-up in days for each individual patient is calculated from the date of last dose of study drug for insulin degludec or the date of last dose of study drug + 7 days for LY3209590 to the last study visit date. The duration of the follow-up in days will be summarized (n, mean, standard deviation, minimum, maximum, median, and sum in total patient years) by treatment group.

The duration on study from date of the first study drug to the last study visit date (including the follow-up visit) will also be summarized by treatment group, the following summary statistics will be provided: n, mean, standard deviation, minimum, maximum, median, and sum in total patient years.

A by-patient listing of drug exposure data will be created to provide data for the CSR.

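### The top exposure category in SAP 5.10.1 starts 1 to 2 days above the planned 26-week course, so no row counts the patients who received that course

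*SAP*

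**What the plan says.** SAP 5.10.1 (Study Drug Exposure) defines exposure as an interval between dates. On its start: "Exposure during the treatment period will be calculated from date of first study basal insulin dose". On its end: "the last dose date for insulin degludec, and the last dose date + 7 days for LY3209590". The section does not say whether one day is added to the difference.

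It then asks for the number of patients in a set of exposure ranges. The month-labelled rows run "≥ 30 days (1 month), ≥ 60 days (2 months), ≥ 90 days (3 months), ≥ 120 days (4 months" and finish with "≥ 183 days (6 months) days". Nothing lies between 120 and 183 days.

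The protocol fixes the planned course:

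- Synopsis 1.1 gives its length: "Study Period 2: treatment period, 26 weeks".
- Section 4.1.1 places the first dose at the randomization visit, Week 0: "Study personnel will inject the first dose of IP at the study site".
- Section 6.7.1 gives its end: "The last study treatment administration for patients treated with LY3209590 will be at Week 25 and for patients treated with insulin degludec the evening before"; this refers to the Week 26 visit.
- Footnote c of the Schedule of Activities agrees, placing Visit 20 about a week after the final LY3209590 injection and a day after the final degludec injection. The schedule allows ±3 days for that visit.

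**The concern.** In a 26-week trial, a top row labelled 6 months will be read as the count of patients who received the full course. Under the SAP's own definition, a patient who takes every dose on its planned day can fall short of it. That patient is then counted no higher than the ≥120-day row, together with someone who stopped after four months. No row separates the two.

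The synopsis gives readers a reason to look at this table: "The study will last 26 weeks to have an adequate duration of exposure necessary to positively exclude any increase in ALT". A study report could therefore show few patients at six months although most completed. Depending on an unstated counting rule, it could also show the arms apart for a reason unrelated to treatment.

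**Working it through.** **Where 183 comes from.** The note to SAP Table BDCL.1 uses a year of 365.25 days. Half of that is 365.25 / 2 = 182.6, which rounds to 183, so the figure is a fair half-year. It matches neither the planned course (26 × 7 = 182) nor the 30-day months of the lower rows (6 × 30 = 180).

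**Planned exposure, first dose at day 0.**

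- LY3209590: last dose at Week 25, day 25 × 7 = 175; exposure 175 + 7 = 182 days.
- Degludec: last dose the day before Week 26, day 26 × 7 − 1 = 181; exposure 181 days.

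With elapsed days, both are below 183, by 1 and 2 days. With one day added they become 183 and 182, so LY3209590 reaches the row and degludec does not.

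**Spread over the Visit 20 window.** Let Visit 20 fall on day 182 + w, with w from −3 to +3, and let the last LY3209590 dose stay 7 days before the visit. Exposure is then 182 + w for LY3209590 and 181 + w for degludec.

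| Count | LY3209590 range | Visit days at ≥183 | Degludec range | Visit days at ≥183 |
|---|---|---|---|---|
| Elapsed | 179–185 | 3 of 7 | 178–184 | 2 of 7 |
| One day added | 180–186 | 4 of 7 | 179–185 | 3 of 7 |

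The gap between arms is 1/7, about 14 percentage points if visits are spread evenly over the window.

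**If the last LY3209590 dose stays on day 175 whatever the visit date.** LY3209590 qualifies on 0 of 7 days (elapsed) or 7 of 7 (one day added), against the same 2 of 7 or 3 of 7 for degludec. The gap can then be large, and its direction depends on the counting rule.

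**Other cut-offs, with dosing moving with the visit.**

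- ≥180 days: patients exactly on schedule qualify in both arms under either rule. Over the window, LY3209590 qualifies on 6 of 7 days and degludec on 5 of 7 (elapsed), or 7 and 6 (one day added).
- ≥178 days: the earliest in-window values are 182 − 3 = 179 for LY3209590 and 181 − 3 = 178 for degludec, so all 7 days qualify in both arms under either rule. If LY3209590 stays on day 175, its 182 days also qualify. An LY3209590 patient whose last dose was given on schedule at Week 24 has 24 × 7 + 7 = 175 days and is correctly left out.

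**The case against.** The best defence is that the row decides nothing. It is one line of a descriptive table. SAP 5.10.1 specifies no test on it, and the SAP revision history records that the t-test on exposure was removed. The section also reports exposure in days by arm, total patient-years, time on study and a by-patient listing, and SAP 5.2 reports discontinuations by arm. A reader of the whole report would see exposure close to 182 days. All of this stands, and it makes the point minor. It does not make the row informative.

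A second defence is that 183 days is a correct conversion of half a year. That also stands. A reader might infer a miscalculation, but the documents show a cut-off that does not fit the course, beside lower rows built on 30-day months.

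A third defence is that real dates will vary. Protocol 6.1.1 lets a missed LY3209590 dose be given up to 3 days late, and Appendix 10 allows extended visit windows. Some completers will therefore pass 183 days, but they do so because of visit and dose timing, which is the difficulty with the row.

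Two stronger inferences are tempting. One is a large false difference between arms. A contrast of all against none needs both an added day that the SAP does not state and every patient exactly on time. The like-for-like gap over the window is 1/7, and it grows only if LY3209590 dosing does not move with Visit 20. The other is that the assessment of ALT is weakened. SAP 5.10.5.2 answers that question with its own models and elevation categories, none of which uses an exposure category.

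**Conclusion.** The point holds at minor severity. By the SAP's definition the planned course yields 182 days (LY3209590) and 181 days (degludec), against a top row of 183. Patients exactly on schedule miss it in both arms with elapsed counting, and in degludec alone if a day is added. Because the next row is 120 days, the table cannot show how many patients received the planned course. Protocol 9.2 expects that to be about 100 of 125 per arm.

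The arm difference is likely to be modest: 3/7 against 2/7 of visit days, or 4/7 against 3/7. This assumes an even spread of visits over ±3 days and a last LY3209590 dose 7 days before Visit 20. Its size and direction change with those assumptions and with the counting rule, so no single figure should be predicted.

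The effect stops at this table. The primary analysis, power, patient-years, hypoglycemia rates and ALT analyses do not use the category.

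**What to change.** In SAP 5.10.1 and its table shell:

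1. Replace the ≥183-day row, or supplement it, with ≥178 days, labelled as the planned 26-week course. This is the lowest in-window value for a completer in either arm.
2. State whether one day is added when exposure is computed.

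A cut-off of ≥180 days would match the 30-day months of the other rows and admit patients exactly on schedule in both arms. It would still miss some early in-window visits and keep the 1/7 gap, because the one-day offset comes from the arm-specific end dates and not from the number 183. Visits outside the ±3-day window are not guaranteed to qualify under any of these cut-offs.

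The cost is one number, one label and one sentence. No data collection or other analysis changes.

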5.10.2. Adverse Events

Adverse events will be summarized as TEAEs (defined as events that are newly reported after the first dose of study basal insulin or reported to worsen in severity from baseline) and compared between treatments unless otherwise specified. The Medical Dictionary for Regulatory Activities (MedDRA) Lowest Level Term (LLT) will be used in determining the treatment-emergent status. The maximum severity for each LLT during the baseline period will be used as baseline severity. All analysis will be performed on the data collected from the date of first dose of study drug (or the randomization visit date if date of first dose is not available) to the end of the study (up to Visit 801).

The incidence of patients with at least 1 TEAE and the incidence of TEAEs by PT and system organ class (SOC) will be presented by treatment group. The number and percentage of patients with TEAEs will be summarized by treatment using MedDRA PTs nested within SOC. Events will be ordered by decreasing frequency within SOC.

The number and percentages of patients with TEAEs ($\geq 2\%$ before rounding) will be summarized by treatment using MedDRA PT (without regard to SOC). Events will be ordered by decreasing frequency.

The incidence of participants with at least 1 TEAE assessed as possibly related to the IP will be summarized by treatment group using MedDRA PT nested within SOC. Events will be ordered by decreasing frequency within SOC. In addition, a summary of TEAEs by maximum severity will be presented descriptively by treatment group.

Discontinuations due to AEs will be summarized by PT and compared between treatment groups using Fisher's exact test for the Safety Population.

All SAEs (including death) will be listed by patient for the Safety Population.

Summary of TE-SAEs similar to summaries for the proportion of patients experiencing each reported TEAE by SOC will be included for the Safety Population.

5.10.3. Adverse Events of Special Interest (AESI)

Summary and analysis of TEAEs related to the following adverse events of special interest (AESIs) is specified in this section:

- deaths and nonfatal cardiovascular events
- hypoglycemia events
- hepatobiliary events
- injection site reactions
- systematic hypersensitivity reactions

5.10.3.1. Death and Nonfatal Cardiovascular Events

Deaths and nonfatal cardiovascular AEs will be adjudicated by an independent Clinical Endpoint Committee with cardiology expertise. The following events will be adjudicated and listed by patient for the Safety Population: death due to cardiovascular events, myocardial infarction, hospitalization for unstable angina, hospitalization for heart failure, coronary interventions (such as coronary artery bypass graft or percutaneous coronary intervention), and cerebrovascular events, including cerebrovascular accident (stroke) and transient ischemic attack. The actual term and PT of the event, date of first dose and last dose of study drug, result of adjudication, and time from first dose to event will be listed.

5.10.3.2. Hypoglycemia Events

According to the 2020 American Diabetes Association standard of medical care in diabetes, there are two levels of hypoglycemia defined by glucose concentration:

- Level 1: glucose <70 mg/dL (3.9 mmol/L) and glucose \geq 54 mg/dL (3.0 mmol/L)
- Level 2: glucose <54 mg/dL (3.0 mmol/L)

With the above glucose reading requirement for Level 1 and 2 hypoglycemia, the following type of hypoglycemia events will be derived: documented hypoglycemia, documented nocturnal hypoglycemia (occurs between bedtime and waking), and documented non-nocturnal hypoglycemia (occurs between waking and bedtime).

Per the study protocol, severe hypoglycemia is reported as a serious AE. Severe hypoglycemia is defined in the protocol and is consistent with the ADA definition, but also requires investigator confirmation of neurological impairment. The 2020 American Diabetes Association standard of medical care in diabetes also classified severe hypoglycemia as Level 3 hypoglycemia. During a severe hypoglycemia episode, the participant has an altered mental status and cannot assist in his/her own care, may be semiconscious or unconscious, or experience coma with or without seizures, and may require assistance of another person to actively administer carbohydrate, glucagon, or other resuscitative actions. This information will be collected in the patient eDiary and the severe hypoglycemia will be listed.

[Table BDCL.1](#) provides the summary of statistical method for hypoglycemia event related analysis. Additionally, severe hypoglycemia events will be listed. The severe hypoglycemia reported as spontaneous AE in the eCRF will also be summarized by MedDRA PT. The Level 2 and Level 3 are usually considered as clinically significant hypoglycemia. Therefore, the analysis on a composite of Level 2 and Level 3 (denoted as Level 2/3) hypoglycemia will also be conducted.

Table BDCL.1. Hypoglycemia Event Related Analyses

Endpoint	Time Point*	Statistical Method
Rate of hypoglycemia events for Level 1 and Level 2/3 
 • Documented • Nocturnal • Non-Nocturnal 	0-12, 0-26, 12-26 weeks, post-treatment period (up to Visit 801)*	Exposure-adjusted rate per year / 100 years (calculated by total number of events divided by total exposure for individual patients) will be provided and the empirical method (see Appendix 1 for details) will be used for treatment comparison.
Incidence of hypoglycemia events for Level 1 and Level 2/3 
 • Documented • Nocturnal • Non-Nocturnal 	0-12, 0-26, 12-26 weeks, post-treatment period (up to Visit 801)*	Logistic regression will include treatment, baseline HbA1c in the model. Note that the logistic regression will be conducted when ≥ 10 patients with this event.

 • Proportion of patients with HbA1c <7% without documented nocturnal hypoglycemia event (Level 1 and Level 2) • Proportion of patients with HbA1c $\leq 6.5\%$ without documented nocturnal hypoglycemia event (Level 1 and Level 2) 	0-26 weeks	Logistic regression will include treatment, country, DPPIV [yes/no], SGLT2 [yes/no], baseline BMI [<30 , ≥ 30], and baseline HbA1c in the model.

Abbreviations: BMI = body mass index; HbA1c = hemoglobin A1c; Level 2/3= Level 2 and Level 3 composite.
Note: The hypoglycemia rate per year during defined period is calculated by the number of hypoglycemia within the period/number of days patient at risk within the period*365.25 days. The hypoglycemia incidence during defined period indicates if the patient has at least 1 hypoglycemia events within the period (Yes/No). The baseline hypoglycemia rate is the rate calculated between Visit 2 and Visit 3.

*Analyses for endpoint during post-treatment period (up to Visit 801) will include all of the data after study drug discontinued on Safety population; analyses for endpoints during other time points will include all data before study drug discontinued on Safety population.

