8.3.7.1. Hypoglycemia

Patients will collect information on episodes of hypoglycemia starting from Visit 2 until the last study visit (Visit 801 or ET visit). For that purpose, patients will be trained about signs and symptoms of hypoglycemia, how to treat hypoglycemia, and how to collect in study diaries appropriate information for each episode of hypoglycemia according to the Schedule of Activities (Section 1.3).

Participants are encouraged to perform SMBG, whenever hypoglycemia may be suspected, either by symptoms experienced or perceived increased risk as related to dietary intake, physical activity, or inadvertent or atypical insulin dosing. All patients will be instructed to treat a SMBG ≤ 70 mg/dL (< 3.9 mmol/L) as hypoglycemia.

Participants will be instructed to report hypoglycemia in the eDiary any time he/she experiences signs or symptoms of hypoglycemia with or without a SMBG ≤ 70 mg/dL (< 3.9 mmol/L).

Severe hypoglycemia is defined as an event requiring assistance of another person to actively administer carbohydrate, glucagon, or other resuscitative actions. During these episodes, the participant has an altered mental status and cannot assist in his/her own care, may be semiconscious or unconscious, or experience coma with or without seizures, and may require parenteral therapy. Glucose measurements may not be available during such an event, but neurological recovery attributable to the restoration of blood glucose concentration to normal is considered sufficient evidence that the event was induced by a low blood glucose concentration (≤ 70 mg/dL [< 3.9 mmol/L]).

If a hypoglycemic event meets the criteria of severe as confirmed by the investigator, it needs to be recorded as serious on the AE eCRF and reported to Lilly as a SAE.

In each case of suspected or confirmed hypoglycemia, it is important that the event be properly categorized, the effect of the intervention be assessed, and the frequency and duration of hypoglycemia be evaluated. The role of dietary changes and physical exercise (or any other contributing factor) in the development of an event should be established. The patient should receive additional education, if deemed appropriate. Management of increased risk of hypoglycemia is described in Section 6.1.2.2.

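### The two HbA1c-target composites in SAP Table BDCL.1 leave out Level 3, so a participant at target whose severe nocturnal event has no qualifying glucose reading can be scored a success

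*SAP*

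**What the plan says.** The last row of SAP Table BDCL.1 (Section 5.10.3.2) holds two responder endpoints over 0 to 26 weeks, both analyzed by logistic regression. One is "Proportion of patients with HbA1c <7% without documented nocturnal hypoglycemia event (Level 1 and Level 2"). The other uses HbA1c ≤6.5% with the same condition, "without documented nocturnal hypoglycemia event (Level 1 and Level 2").

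The text above the table defines the levels. Level 1 is glucose of at least 54 and below 70 mg/dL. Level 2 is likewise a concentration: "Level 2: glucose <54 mg/dL (3.0 mmol/L"). Documented, nocturnal and non-nocturnal events are built from these: "With the above glucose reading requirement for Level 1 and 2 hypoglycemia, the following type of hypoglycemia events will be derived". Severe hypoglycemia is a separate category. The SAP notes that the 2020 American Diabetes Association standard "also classified severe hypoglycemia as Level 3 hypoglycemia", and describes it by mental state and need for help, with no glucose threshold. Protocol 8.3.7.1 adds: "Glucose measurements may not be available during such an event". It accepts neurological recovery once glucose is restored as sufficient evidence.

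Elsewhere in the same SAP section Level 3 is brought in. Because Levels 2 and 3 are usually regarded as clinically significant, "the analysis on a composite of Level 2 and Level 3 (denoted as Level 2/3) hypoglycemia will also be conducted". The incidence row reads "Incidence of hypoglycemia events for Level 1 and Level 2/3", the rate row uses the same levels, and each has a nocturnal line.

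**The concern.** The responder definition has two parts: reaching the HbA1c target, and having no nocturnal hypoglycemia of the named levels. The named levels are exactly those that depend on a meter value. A severe episode at night is a situation in which a value may well not be taken, and the protocol foresees this. As the row is written, one nocturnal reading of 69 mg/dL makes a participant a failure, while a severe nocturnal event without a reading below 70 mg/dL does not.

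The table is also inconsistent with itself. Its rate and incidence rows pair Level 1 with Level 2/3, including for nocturnal events, and the SAP gives no reason for dropping Level 3 from the composites alone. At stake is whether the responder proportions can be read at face value, and whether they agree with the nocturnal Level 2/3 results reported beside them.

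**Working it through.** The documents give no expected responder rate, power statement or severe-event rate for this endpoint, so there is no planned figure to reproduce. The check is of the rule itself, followed by a scale for its effect.

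**Inputs**
- Levels that cause failure: 1 and 2 (SAP Table BDCL.1, composite row).
- Level 1: 54 ≤ glucose < 70 mg/dL. Level 2: glucose < 54 mg/dL (SAP 5.10.3.2).
- Level 3: severe event; a reading is not required (SAP 5.10.3.2; Protocol 8.3.7.1).
- Arm size, for scale only: about 125 randomized and about 100 completing per arm (Protocol 9.2).

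**Rules compared**
- As written: success = HbA1c target met AND no nocturnal Level 1 or Level 2 event.
- With Level 3 added: success = HbA1c target met AND no nocturnal Level 1, Level 2 or Level 3 event.

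**Enumeration.** I crossed target met or not (2), nocturnal reading missing, 45, 60 or 85 mg/dL (4), and severe nocturnal event or not (2), giving 2 × 4 × 2 = 16 cases. The rules disagree in two:

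| Target met | Nocturnal reading | Severe event | As written | With Level 3 |
|---|---|---|---|---|
| yes | missing | yes | success | failure |
| yes | 85 mg/dL (for example, taken after recovery) | yes | success | failure |

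In the other 14 cases they agree. In particular, a severe event with a nocturnal reading of 45 or 60 mg/dL fails under both rules, because the reading itself qualifies as Level 2 or Level 1. A participant who misses the HbA1c target fails under both.

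The score therefore changes only for a participant who (a) meets the HbA1c target, (b) has a severe nocturnal event with no reading below 70 mg/dL, and (c) has no other documented nocturnal Level 1 or 2 event in the period. A second such event in the same participant changes nothing more.

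**Scale.** Overstatement of one arm's responder proportion = k / n, where k is the number of participants meeting (a) to (c).
- k = 1: 1/125 = 0.8 percentage points; 1/100 = 1.0.
- k = 5: 5/125 = 4.0 percentage points; 5/100 = 5.0.

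The documents do not supply k. The range 0 to 5 is an assumption for illustration, and 0 is plausible.

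**Direction.** Within an arm the written rule can only raise the proportion relative to a rule that counts Level 3. For the difference LY3209590 minus degludec, one such participant on LY3209590 moves it by +0.8 points and one on degludec by −0.8 points (n = 125).

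**The case against.** The best defense is that the endpoint is labeled as *documented* nocturnal hypoglycemia, and the SAP ties that word to a glucose reading. A reading-based composite with severe events reported separately is a coherent design, and neither document states that the endpoint must capture every kind of nocturnal hypoglycemia. This has some force. But the adjacent rows also carry documented and nocturnal lines and still include Level 3, so the SAP's own practice does not explain the omission.

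A second defense is that Protocol 6.1.2.2 counts investigator-confirmed severe events as documented hypoglycemia, so Level 3 might be implied. That definition serves the management of increased hypoglycemia risk. The composite row names its levels explicitly, and a programmer would follow the row. What the argument shows is that the term has two meanings across the documents.

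Third, few participants are likely to be affected. The population is insulin-naïve, severe hypoglycemia in the 6 months before screening is an exclusion (Protocol 5.2), and SAP Appendix 1 expects that hypoglycemia data could be sparse. This stands. It limits the size of the effect but leaves the rule unchanged.

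Two stronger readings are tempting. A reader might infer that severe hypoglycemia is dropped from the safety assessment. The documents do not support that: severe events are reported as serious adverse events, listed, summarized by preferred term and counted in the Level 2/3 rates and incidences, and Protocol 9.4.6.3 plans a separate Level 3 analysis. A reader might also infer that every severe nocturnal event without a reading turns a failure into a success. It does so only under conditions (a) to (c).

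**Conclusion.** The composite rows are inconsistent with the rest of Table BDCL.1 and can misclassify a participant. No other text in either document restores Level 3 to them. Each participant who meets all three conditions overstates that arm's responder proportion by about 0.8 percentage points with 125 in the arm, or 1.0 with 100.

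Those denominators are planning figures from Protocol 9.2. The endpoint's actual denominator is less clear: the footnote to Table BDCL.1 places the on-treatment analyses in the Safety Population, which pools former Algorithm 2 participants into the LY3209590 group, while Protocol 9.4.6.3 uses the Efficacy Population for hypoglycemia. The number of affected participants is not given and may be zero.

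The documents do not support saying that the rule favors either treatment, since the between-arm difference depends on where such events fall. The composites appear in neither document's list of objectives and endpoints, so the primary and listed secondary results are untouched. This is a minor point, worth correcting because the rule is wrong in a known direction within each arm and is easy to repair.

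**What to change.** In SAP Table BDCL.1, change the condition in both composites to *without nocturnal hypoglycemia (Level 1 or Level 2/3)*, and state that a nocturnal severe event counts as failure whether or not a glucose reading exists. Add a sentence to Section 5.10.3.2 saying that *documented* in the SAP refers to the reading-based Level 1 and Level 2 events, so that it is not confused with the usage in Protocol 6.1.2.2.

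The cost is a wording change and a small change to the derivation program. Severe events are already collected in the eDiary and reported as serious adverse events, and the nocturnal Level 2/3 lines already require them to be classified by time of day. No new data, model or sample size is needed.
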